8.3.6 Responder rates

QMG, MG-Composite, and MGADL responder rates will be summarized at each assessed post-Randomization Visit (during Dosing Period 1) and compared between the 2 Treatment Groups utilizing Fisher's exact test for each visit for the FAS.

The frequency of attained point improvement will be plotted against treatment for Visit 9 (Week 8). For each point improvement the test result will be displayed in a table and in the plot.

8.3.7 Single Fiber Electromyogram

Jitter (SFEMG) results will be listed, including change from Baseline.

Three variables will be further analyzed; MCD of the IPI accepted after external review, % Normals accepted after external review and % Blocking accepted after external review. For these variables the listing will include change from baseline. In addition, for these variables observed values and change from baseline will be summarized using descriptive statistics, by treatment group and visit, including changes from Baseline for the FAS.

Change from baseline line MCD accepted after external review will be plotted against change from baseline in efficacy variables, QMB, MG-composite and MGADL.

Clinically meaningful improvement in jitter (SFEMG) will be calculated upon MCD of the IPI accepted after external review. Clinically meaningful improvement, defined as a reduction in

MCD of at least 9us, will be flagged in the listing. Contingency tables will be created of jitter (SFEMG) clinically meaningful improvement against QMG, MG-composite and MGADL responders by treatment.

8.3.8 Correlation analysis

Pearson correlation of patient reported outcomes (PROs) with IgG levels and association using Spearman's correlation with [REDACTED], [REDACTED] and [REDACTED] status will be displayed by visit. In addition Pearson correlation of the clinical assessment of disease activity (variables QMG and MG composite), disease severity (MGFA) and patients' assessment on impact on daily life (MG-ADL) will be displayed for each visit. This analysis will be repeated using baseline corrected values of the PROs and the variables QMG, MG composite, MGFA and MG-ADL.

Further association between PROs will also be investigated using Pearson correlation.

8.3.9 Psychometric analyses

The Psychometric analyses of the newly developed measures MG muscle weakness severity and fatigability and fatigue scales will be performed blinded from treatment arms. This psychometric analysis of the MG muscle weakness severity and fatigability scale and fatigue scale will be performed by a vendor using Rasch analysis and will be reported separately from the CSR. For these analyses a separate psychometric analysis plan will be written. Subsequently, the data will be further analysed using Rasch models, with the aim to decrease the number of items and develop a scoring algorithm, this is not described in this SAP and will not reported in the CSR.

9 PHARMACOKINETICS AND PHARMACODYNAMICS

9.1 Pharmacokinetics

The PK variable is the plasma concentration of UCB7665. Pharmacokinetic parameters such as Cmax and area under the curve will not be derived (eg, by non-compartmental analysis) due to the limited sampling performed at each visit.

Individual concentrations of UCB7665 will be listed for the SS and summarized for the PK-PPS at each scheduled time point. In the listing relative and absolute time will be displayed. Relative time of pre-dose samples will be relative to start of infusion and display pre-dose for samples prior to dosing and display actual relative time for samples not prior to dosing. Relative time of post-dose samples will be relative to end of infusion. Descriptive statistics of concentrations will be calculated only if at least two thirds of the individual data points are quantifiable (\geq LLOQ). Summaries will include the number of available observations, mean, median, SD, minimum, maximum, geometric mean, and geometric coefficient of variation (assuming log-normally distributed data). Values below the LLOQ will be reported with a clear sign indicating that they were below the LLOQ. Individual concentrations of UCB7665 will also be displayed graphically on a linear and on a semi-log scale. UCB7665 concentrations also be displayed in a spaghetti plot by treatment group on a linear and on a semi-log scale. In the spaghetti plot, time will

9.2 Pharmacodynamics

The analysis of the PD data will be performed on the FAS with the exception of the total serum IgG and IgG subclasses results, which will be analyzed on the PD-PPS. All listings will be presented for the SS.

Any values that are BLQ or ALQ will be handled as described in [Section 4.2.2](#).

All analyses described in this section will be performed on the PD-PPS.

9.2.1 Total serum IgG and IgG subclasses

Total serum IgG concentrations and IgG subclasses will be listed by treatment and time point including changes from Baseline and percentage changes from Baseline. Descriptive summaries (including n, arithmetic mean, median, SD, minimum and maximum) will be presented by treatment group and time point for absolute values, changes from Baseline and percentage changes from Baseline. The maximum decrease from Baseline in total serum IgG (absolute and percentage decrease) will be reported in the listing and summarized for each treatment.

In the event that a decrease from Baseline in total serum IgG is not observed in a given subject, the maximum decrease will be reported as the smallest increase from Baseline. Mean and mean percentage change from Baseline values in total serum IgG will be plotted over time by treatment and period with all treatments overlaid on the same plot.

9.2.2 MG-specific autoantibodies

MG-specific autoantibodies [REDACTED] will be listed by treatment and time point including changes from Baseline and percentage changes from Baseline. Descriptive summaries (including n, arithmetic mean, median, SD, minimum and maximum) will be presented by treatment group and time point for absolute values, changes from Baseline and percentage changes from Baseline.

Mean and mean percentage change from Baseline values in MG-Specific autoantibodies will be plotted over time by treatment and period with all treatments overlaid on the same plot.

10 IMMUNOLOGICAL ANALYSES

All analyses described in this section will be based on the SS.

10.1 Immunoglobulins

Immunoglobulins (IgE, IgA and IgM) will be listed by treatment group and time point including changes from Baseline. Descriptive summaries will be presented by treatment group and time point for both absolute values and changes from Baseline.

Individual figures over time (absolute value) will be presented by subject, with all variables overlaid on the same plot and separate plots each subject.

Any values that are BLQ or ALQ will be handled as described in [Section 4.2.4](#).

10.2 [REDACTED]

Immunological variables will be analyzed for all subjects in the SS. [REDACTED] data will be summarized at each scheduled visit, and the rate of [REDACTED] positive subjects will be calculated.

Dependent on availability the intention is to use a [REDACTED] screening assay without a calibrator. A cut point will be determined by the bioanalytical laboratory that will be used to determine the status of [REDACTED] as above the cut point (ACP) or below the cut point (BCP). A calibrator screening assay currently in place to measure [REDACTED] as relative mass units (RMU) in units/mL will be used in the event that the newer screening assay is unavailable.

A cut point will be determined by the bioanalytical laboratory that will be used to determine the status of [REDACTED] as above the cut point (ACP) or below the cut point (BCP). For any [REDACTED] levels that are ACP, a further confirmatory assay will be performed, the results of which will be determined as either 'confirmed positive' (CP) or 'not confirmed positive' (NCP). In the case of the newer screening assay; for samples that are CP a further titre assay will be performed and the [REDACTED] titre reported. In lieu of the newer screening assay, the RMU result from the calibrator screening assay will be used to report [REDACTED] levels.

The results for the [REDACTED] measurements will be listed by treatment group and time point based on the SS, including the screening assay, confirmatory assay and either the titre or level in units/mL (as applicable).

The following definitions will be applied:

- An [REDACTED] status of positive will be concluded for any subject with an [REDACTED] level that is ACP and CP at any time point
- An [REDACTED] status of negative will be concluded for any subject with an [REDACTED] level that is either BCP or ACP and NCP at any time point
- A subject will be classified as having [REDACTED] positivity at Baseline if the Day 1, predose result is ACP and CP
- A subject will be classified as having treatment-induced [REDACTED] positivity when meeting one of the following criteria:
 - The Baseline result is either BCP or ACP and NCP, and at least one post-Baseline time point is ACP and CP
 - The Baseline result is positive (ACP and CP) and at least one post-Baseline measurement shows a pre-defined fold increase in titre or units/mL (as applicable) from the Baseline value (the fold increase from Baseline required to meet this criteria will be defined with the development of the assay and will be included in the TFLs)
- A subject will be classified as overall positive if at least one post-Baseline measurement is ACP and CP (this includes subject who have negative results at Baseline)
- A subject will be classified as overall negative if at all post-Baseline visits the [REDACTED] status is negative (this includes subjects who have positive [ACP and CP] results at Baseline)

The [REDACTED] status (positive/negative) will be summarized as a categorical endpoint (number and percentage of subjects) for all time points and overall, based on the SS.

In addition, the first occurrence of treatment-induced [REDACTED] positivity (based on the definitions above) will be summarized (number and percentage of subjects) at each post-Baseline visit, based on the SS. This tabulation will count the number of subjects at each post-Baseline visit who fulfill at least one of the above defined criteria for treatment-induced positivity; subjects will be counted in the numerator based on the earliest visit at which one of these criteria is fulfilled. At other visits, subjects will be counted in the denominator (assuming a measurement is available). For all tabulations, percentages will be based on the number of observations at each visit.

A separate listing will be presented (based on the SS) showing the UCB7665 concentrations and [REDACTED] measurements in the same output in adjacent columns. The listing will include the UCB7665 concentration, [REDACTED] status (ACP or BCP) and confirmatory assay results if applicable (NCP or CP), together with the titre or units/mL (as applicable) for results that are CP. In addition the time since the previous administration of IMP will be reported (in days).

Finally, individual subject plots (based on the SS) will be presented displaying the [REDACTED] titre or units/mL (as applicable) and UCB7665 concentrations overlaid on the same figure. The figure will also show the timing and dose of each administration of UCB7665 received during the study. The [REDACTED] titre data will be plotted using a semi-logarithmic scale.

The rules for handling values that are BLQ in the UCB7665 concentration data are described in [Section 4.2.5](#). For the [REDACTED] data, any negative results for which there are no titres or units/mL (as applicable) available at a specific visit will be substituted with 0.001 for the purpose of the figure.

10.3 Serum complement levels and plasma complement levels

Serum (C3 and C4) and plasma (C3a and C5a) complement variables will be listed by treatment group and time point including changes from Baseline. Descriptive summaries (including n, arithmetic mean, median, SD, minimum and maximum) will be presented by treatment group and time point for both absolute values and changes from Baseline.

Any values are that BLQ or ALQ will be handled as described in [Section 4.2.4](#).

10.4 Serum BAFF levels

Serum BAFF levels will be listed by treatment group and time point including changes from Baseline. Descriptive summaries (including n, arithmetic mean, median, SD, minimum and maximum) will be presented by treatment group and time point for both absolute values and changes from Baseline.

Any values are that BLQ or ALQ will be handled as described in [Section 4.2.4](#).

10.5 Cytokines

Cytokines will be listed by treatment group and time point, changes from Baseline will be added to the listing. Descriptive summaries (including n, arithmetic mean, median, SD, minimum and maximum) will be presented by treatment group and time point for both absolute values and changes from Baseline, both for all subjects and for subjects experiencing infusion reactions.

Any values are that BLQ or ALQ will be handled as described in [Section 4.2.4](#).

10.6 [REDACTED]

[REDACTED] will be listed by treatment group and time point. I subjects experiencing infusion reactions changes from Baseline will be added to the listing. For subjects experiencing infusion reactions, descriptive summaries (including n, arithmetic mean, median, SD, minimum and maximum) will be presented by treatment group and time point for both absolute values and changes from Baseline.

Any values are that BLQ or ALQ will be handled as described in [Section 4.2.4](#).

11 SAFETY ANALYSES

All safety analyses will be presented using the SS. Listings will be presented by Dosing Period, treatment group and subject; tabulations will be presented by Dosing Period and treatment group in the following order:

Dosing Period 1:

- Placebo
- UCB7665 7mg/kg

For Dosing Period 2 and the Observation Period the following treatment groups will be considered for analysis and will be displayed as such in the TFLs (the first two groups will only be utilized for observation period in case patients do not receive any dosing in period 2):

- Placebo
- UCB7665 7mg/kg
- Placebo - UCB7665 7mg/kg
- Placebo - UCB7665 4mg/kg
- UCB7665 7mg/kg - UCB7665 7mg/kg
- UCB7665 7mg/kg - UCB7665 4mg/kg

11.1 Extent of exposure

All drug administration details (including date, start and stop time of infusion, location of infusion site, interruptions, discontinuations, body weight, dose, volume delivered, percent of planned dose) will be listed using the SS. The reasons for any interruptions or discontinuations will be included in the listing. The duration of the infusion, in minutes, will also be calculated.

The percent of planned dose administered will be calculated based on the actual volume delivered as follows:

$$\text{Percent of planned dose (\%)} = (\text{Actual volume}/\text{Planned volume}) * 100$$

For all subjects the planned volume is 10mL.

In Dosing Period 1 subjects will be randomized (1:1) to receive one of the following treatments:

- 3 sc doses of UCB7665 7mg/kg at 1 week intervals
- 3 sc doses of placebo at 1 week intervals

In Dosing Period 2 subjects will be rerandomized (1:1) to receive one of the following treatments:

- 3 sc doses of UCB7665 7mg/kg at 1 week intervals
- 3 sc doses of UCB7665 4mg/kg at 1 week intervals

The randomization in Dosing Period 2 will be stratified by the treatment received in Dosing Period 1.

11.2 Adverse events

Adverse events will be recorded from the time of informed consent until study completion. All AEs will be coded ([Section 3.8](#)) and categorized by relationship to UCB7665.

In addition, AEs will be classified according to the Common Terminology Criteria for Adverse Events (CTCAE) Version 4.03 for severity. For any AEs where it is not possible to provide a CTCAE grading, the events will be assessed using a standard intensity classification (mild, moderate and severe).

A TEAE is defined as any event that was not present prior the first administration of IMP or any unresolved event already present before the first administration of IMP that worsens in intensity following exposure to treatment. Adverse events starting before the first administration of IMP or after 8 weeks following the final dose of IMP will not be considered TEAEs. Thus AEs before first dosing and AEs after 8 weeks following the final dose will be combined in one category. Such events will be listed only.

Where dates are missing or partially missing, AEs will be assumed to be treatment-emergent. Handling of missing dates/times for classification of AEs as TEAEs is described in [Section 4.2.7](#).

The following rules will be used to assign a TEAE to a study period:

- Dosing Period 1: a TEAE will be assigned to Dosing Period 1 for the tabulations if the start date/time of the event is at the time of or after the first administration of IMP on Day 1, up to the time of actual first administration of IMP in Dosing Period 2 (planned for Day 29)
- Dosing Period 2 or Observation Period: a TEAE will be assigned to 'Dosing Period 2 or Observation Period' for the tabulations if the start date/time of the event is at the time of or after the first administration of IMP (planned for Day 29), until 8 weeks following the final dose; events starting later than 8 weeks following the final dose of IMP are not considered TEAEs

In the case of early withdrawal in either Dosing Period 1 or 2, a TEAE will be assigned to the respective Dosing Period based on the last received infusion.

The number and percentage of subjects who experience TEAEs will be summarized for each Dosing Period and treatment group. In all tabulations, TEAEs occurring during the Observation Period will be presented as part of Dosing Period 2. In addition summaries for total active and all treatments will be created. The following summaries will be presented:

- Incidence of TEAEs (overview including number and percentage of subjects with any TEAEs, serious TEAEs, discontinuations due to TEAEs, related TEAEs, TEAEs with CTCAE Grade 3 and above [or rated as 'severe' for events with no CTCAE classification], and deaths; event counts will also be included)
- Incidence of TEAEs by SOC, HLT and PT
- Incidence of TEAEs during the Dosing Period by SOC, HLT and PT
- Incidence of serious TEAEs by SOC, HLT and PT
- Incidence of non-serious TEAEs by SOC, HLT and PT
- Incidence of AEs of special interest by SOC, HLT and PT

-
- Incidence of AEs of interest by SOC, HLT and PT
 - Incidence of TEAEs by relationship, SOC, HLT and PT
 - Incidence of serious TEAEs by relationship, SOC, HLT and PT
 - Incidence of non-serious TEAEs by relationship, SOC, HLT and PT
 - Incidence of fatal TEAEs by relationship, SOC, HLT and PT
 - Incidence of TEAEs by maximum relationship, SOC, HLT and PT
 - Incidence of TEAEs by maximum intensity (mild, moderate and severe), SOC, HLT and PT
 - Incidence of non-serious TEAEs above threshold of 5% of subjects by SOC and PT
 - Incidence of non-serious TEAEs above threshold of 5% of subjects by relationship, SOC and PT
 - Discontinuation due to AEs

Summary tables will contain counts of subjects, percentages of subjects in parentheses and the number of events. A subject who has multiple events in the same SOC, HLT and PT will be counted only once in the subject counts but all events will be included.

In the TEAEs above threshold of 5% only those AEs will be included which are present at 5% of the subjects within a treatment group.

Adverse event summaries will be ordered by alphabetical SOC, alphabetical HLT within SOC and decreasing frequency of PT in the 'Period 2 UCB7665 7mg/kg - UCB7665 7mg/kg' column for tables.

A listing will be presented by treatment group and subject for all AEs. This will include the onset date/time and outcome date/time of the event (including relative days), the AE duration, days since first dose of IMP, days since most recent dose of IMP, pattern of event, severity/intensity, relationship, action taken and outcome. In addition the listing will flag AEs that led to discontinuation, TEAEs, serious adverse events (SAEs), AEs of interest, AEs of special interest and infusion reactions.

AEs of interest are:

- Severe headache
- Moderate to severe diarrhea
- Moderate to severe abdominal pain
- Moderate to severe vomiting

AEs of special interest are Potential Hy's Law, defined as $\geq 3x$ upper limit of normal (ULN) Alanine aminotransferase (ALT) or Aspartate aminotransferase (AST) with coexisting $\geq 2x$ ULN total bilirubin in the absence of $\geq 2x$ ULN alkaline phosphatase (ALP), with no alternative explanation for the biochemical abnormality.

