3.2.2 Study periods

The maximum duration of the study per subject will be approximately 18 weeks, consisting of the following 3 periods:

- Screening Period: 1 to 28 days
- Treatment Period: 6 weeks
 - Dosing Period 1 of 4 weeks. This period will start at the first actual dosing of Period 1.
 - Dosing Period 2 of 2 weeks. This period will start at the first actual dosing of Period 2.
- Observation Period: 8 weeks

The end of the study is defined as the date of the final clinic/hospital visit of the final subject in the study.

In the case a subject does not receive dosing in Dosing Period 2, the rule for entering the Observation Period given in [Section 2.3](#) will be generalized such that the subject will enter the Observation Period the day after the last dosing of Dosing Period 1. All data up to the missed dose will be treated according to plan, including data planned on the dosing day prior to the actual dosing.

The following definitions for starting and entering the study periods will be applied:

- Started period 1 is defined as all subjects in the safety set. Completed period 1 includes those subjects who have completed assessments prior to the first study treatment of Period 2 (Day 29).
- Started period 2 is defined as having received treatment on Period 2 Day 29. Completed period 2 includes those subjects who have completed assessments on Observation Period Day 50.
- Started Observation Period is defined as having assessments on Observation Period Day 50. Completed observation period includes those subjects who have a completed status in the study termination case report form

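### For subjects who get no Dosing Period 2 infusion, SAP 11.2 and SAP 3.2.2 place later TEAEs in different periods, so the Period 1 adverse event tables depend on which is followed

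*SAP*

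**What the plan says.** SAP 11.2 (Adverse events) sets the TEAE window by exclusion: "Adverse events starting before the first administration of IMP or after 8 weeks following the final dose of IMP will not be considered TEAEs". Its Dosing Period 1 bullet runs from the first dose "up to the time of actual first administration of IMP in Dosing Period 2 (planned for Day 29"). The bullet for Dosing Period 2 or Observation Period starts at that same infusion. A further sentence reads: "In the case of early withdrawal in either Dosing Period 1 or 2, a TEAE will be assigned to the respective Dosing Period", with the last infusion received as the criterion.

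SAP 3.2.2 (Study periods) has a different rule for a subject with no Period 2 dosing: "the subject will enter the Observation Period the day after the last dosing of Dosing Period 1". It then adds a carve-out: "All data up to the missed dose will be treated according to plan".

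SAP 11 (Safety analyses) adds a Placebo column and a UCB7665 7mg/kg column to the Dosing Period 2 and Observation Period display, to "be utilized for observation period in case patients do not receive any dosing in period 2". SAP 11.2 also states: "In all tabulations, TEAEs occurring during the Observation Period will be presented as part of Dosing Period 2".

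The SAP's own change list (section 15.1.2, Changes 1, 2 and 7) shows that Amendment 1 introduced these columns. It records no change to the period-assignment rule in 11.2. Protocol 14.4.1 assigns an AE by its start relative to the first dose received in the respective period, and does not address a subject who never receives a Period 2 dose.

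**The concern.** Take a subject who stops in Period 1 and has a new TEAE five weeks after the last dose. Under the early-withdrawal sentence it is a Period 1 event. Under 3.2.2 the subject is already in the Observation Period, and the event belongs in one of the added columns under Dosing Period 2. A programmer following the SAP could do either.

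Dosing Period 1 is the only part of the study with a concurrent randomized placebo group. Stopping is also tied to outcome: Protocol 6.4 requires IMP discontinuation for, among other things, related severe headache or GI events and rescue therapy. If the rule is settled after unblinding, the choice could be influenced by the results. If 11.2 is applied as written, stoppers are watched in Period 1 for longer than continuers.

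**Working it through.** The plan gives no figure to reproduce here. The check is a comparison of the rules followed by day counts.

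**Inputs.** Planned infusions on Days 1, 8 and 15, and the first Period 2 infusion on Day 29 (Protocol Table 5.1). TEAE window to 56 days after the last dose (SAP 11.2). 42 subjects randomized 1:1 (SAP 2.3), so 42 / 2 = 21 per arm.

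**Where the rules agree.** I read the carve-out in 3.2.2 as keeping data in Period 1 until the first planned dose that is missed. Under 11.2 those data are in Period 1 as well. An event that leads to the stop starts before that missed dose, so it is a Period 1 event either way.

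**Where they differ.**
- TEAE window end = last dose day + 56.
- Period 1 window under 11.2 = last dose day − 1 + 56.
- Period 1 window under 3.2.2 = first missed dose day − 1.
- Days in dispute = window end − first missed dose day.

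| Last dose | First missed dose | Window ends | Period 1 days, 11.2 | Period 1 days, 3.2.2 | Days in dispute |
|---|---|---|---|---|---|
| Day 1 | Day 8 | Day 57 | 56 | 7 | 49 |
| Day 8 | Day 15 | Day 64 | 63 | 14 | 49 |
| Day 15 | Day 29 | Day 71 | 70 | 28 | 42 |

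A continuer has 29 − 1 = 28 days in Period 1. The 11.2 windows for stoppers are therefore 56 / 28 = 2.0 to 70 / 28 = 2.5 times as long.

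If the missed dose in 3.2.2 is taken to mean the Day 29 infusion in every case, the disputed spans become 57 − 29 = 28, 64 − 29 = 35 and 71 − 29 = 42 days. The conflict remains, but is smaller for those who stop after dose 1 or 2.

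**Weight of one subject.** 1 / 21 = 4.8% and 2 / 21 = 9.5%. SAP 11.2 includes tables of non-serious TEAEs restricted to terms reaching 5% of a treatment group. One subject falls below that line and two fall above it, so one reassigned subject can decide whether a term appears.

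**How many subjects.** The documents do not say. For an assumed Period 1 stopping rate d, the expected number is 42d and the chance of at least one is 1 − (1 − d)^42.

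| Assumed d | Expected stoppers | Chance of at least one |
|---|---|---|
| 2% | 0.8 | 57% |
| 4.8% | 2.0 | 87% |
| 10% | 4.2 | 99% |
| 15% | 6.3 | >99% |

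**The case against.** The best reply is that 11.2 is the AE-specific section and is nearly self-sufficient. Its Period 1 bullet ends only at a Period 2 infusion, which never happens for these subjects; its Period 2 bullet cannot start; the early-withdrawal sentence gives the same answer; and Protocol 14.4.1 is compatible with it. Section 3.2.2 is then a general definition. The added columns are a layout for all safety tables, including laboratory data by time point, so an empty AE column would not be a contradiction.

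This carries weight, but it does not close the matter. The sentence about all tabulations is in 11.2 too, so precedence of the AE section cannot settle it. If 11.2 does govern, the unequal windows in the table above become the plan rather than an ambiguity.

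Other points stand and limit the concern. No inferential AE test is specified. The AE listing gives onset dates and days since the first and most recent dose, so either allocation can be rebuilt. Visits after stopping are only encouraged (Protocol 6.4 and 8.5), so the 56 to 70 days are upper bounds.

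A reader might infer more than the documents support:
- *The whole 8 weeks is in dispute.* It is not; the first 7 to 14 days after the last dose are in Period 1 under both rules.
- *Events that force a stop drop out of the placebo comparison under 3.2.2.* They start before the missed dose and count either way, and a subject counts once per term.
- *The active arm is inflated.* This needs stoppers to be mostly on active drug. The documents do not show that, and rescue-driven stops could fall on placebo.
- *The added columns can never hold a TEAE.* This is too strong. Someone who completes the Day 29 assessments but is not dosed has completed Period 1 under 3.2.2 and is arguably not an early withdrawal, although the Period 1 bullet would still keep that subject's events in Period 1.

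**Conclusion.** The conflict is in the current text and should be resolved before unblinding. It covers TEAEs starting after the first missed dose in subjects with no Period 2 infusion: about 42 to 49 of the 56 days after the last dose, on the reading of 3.2.2 set out above. It can change later new terms, later SAEs and event counts in the descriptive Period 1 tables, by 4.8 points per subject in an arm of 21. It does not change whether the event behind the stop is counted, and the direction of any effect between arms cannot be inferred. If 11.2 is followed, a second defect arises: up to 56 to 70 days in Period 1 for stoppers against 28 for continuers. The practical size depends on the number of stoppers; about 1 to 6 of 42 is an assumption, not a documented figure.

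**What to change.** In SAP 11.2, give the Period 1 tables one end point for every Safety Set subject, whether or not IMP was stopped: the first Period 2 infusion or, if none is given, the planned Visit 9 date (Day 29). Show these subjects' later TEAEs, to 8 weeks after the last dose, in the Placebo and UCB7665 7mg/kg Observation columns already planned. Drop the last-infusion sentence as it applies to Period 1, and align 3.2.2.

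Everyone then has the same planned 28-day Period 1 window and no event is lost. This is a new common cut-off: it replaces the 11.2 rule and, for those stopping after dose 1 or 2, runs longer than the 3.2.2 window as tabulated above.

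The cost is SAP wording and one derivation, with no new data. The downside is that the Observation columns will hold few subjects, so their percentages will be unstable; counts should be read alongside them.
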